#### PROMIS FATIGUE SHORT FORM 6A

The PROMIS Fatigue Short Form 6a is a validated PRO instrument measuring the severity of

fatigue in participants. The PROMIS Fatigue Short Form 6a consists of 6 items in which each item is answered using a 5-point Likert-type scale (1=not at all, 2=a little bit, 3=somewhat,

Fatigue 6a - Adult v1.0		
Short Form Conversion Table		
Raw Score	T-score	SE*
6	33.4	4.9
7	39.1	2.9
8	42.0	2.4
9	44.2	2.2
10	46.1	2.1
11	47.8	2.1
12	49.4	2.1
13	50.9	2.0
14	52.4	2.0
15	53.7	2.0
16	55.1	2.0
17	56.3	1.9
18	57.5	1.9
19	58.8	1.9
20	60.0	1.9
21	61.2	1.9
22	62.4	1.9
23	63.7	2.0
24	65.0	2.0
25	66.4	2.0
26	67.8	2.0
27	69.3	2.0
28	71.0	2.1
29	73.0	2.5
30	76.8	3.8

\*SE = Standard Error on T-score metric

4=quite a bit, 5=very much), and the total score is the sum of the six item scores. Total scores range from 6 (indicating the best health status) to 30 (worst health status). Raw total scores are converted to T-scores using conversion tables (provided in the PROMIS Fatigue scoring manual and shown in the table below), which standardizes the score with a mean of 50 and standard deviation of 10 (a higher T-score indicates worse fatigue).

The PROMIS Fatigue Short Form 6a is completed during Visit 4 and Visit 7/EOT.

The following exploratory efficacy endpoint will be assessed:

- Change from Visit 4 to Visit 7/EOT in the PROMIS Fatigue Short Form 6a T-score

#### miRNA ANALYSIS

A panel of 6 circulating microRNAs (miR-125b-5p, miR-451a, miR-3613-5p, miR-150-5p, miR-342-3p, and let-7b) will be collected at CC/Screening and CCI EOT.

The following exploratory efficacy endpoints will be assessed:

- Change from CC/Screening to CCI/EOT in miRNA expression levels (miR-125b-5p, miR-451a, miR-3613-5p, miR-150-5p, miR-342-3p, and let-7b)

#### 8.5.2. Intercurrent Event Handling and Data Imputation for Exploratory Efficacy Endpoints

See section 8.1.6, no missing data will be imputed for the exploratory efficacy endpoints.

#### 8.5.3. Analysis of Exploratory Efficacy Endpoint(s)

##### ANALYSIS OF ENDOMETRIOSIS-RELATED PAIN (DYS, NMPP, OPP) SCORES

Results for changes from BC to TRC1 and TRC2 will be extracted from the longitudinal analyses used to analyse changes from BC to TRC1, TRC2, and TRC3 (see section 8.3.5).

A similar analysis for the primary efficacy variable described in Section 8.3.7 using ANCOVA will be performed for the change from SC to SFC in the mean OPP score, the mean DYS score, and the mean NMPP score for SFAS.

##### ANALYSIS OF EUROQOL-5 DIMENSIONS 5-LEVEL VERSION (EQ-5D-5L)

A similar analysis for the primary efficacy variable described in Section 8.3.5 using ANCOVA will be performed for the change from BC to TRC3 in EQ-VAS.

The change from BC to TRC3 in each of the five dimensions (Mobility, Self-care, Usual Activities, Pain/Discomfort, and Anxiety/Depression) scores will be summarized by treatment group.

#### ANALYSIS OF INTERFERENCE WITH DAILY ACTIVITIES

A similar analysis for the primary efficacy variable described in Section 8.3.5 using longitudinal model will be performed for the mean change from BC to TRC3 in level of difficulty to do daily activities.

#### ANALYSIS OF WPAI-ENDOMETRIOSIS

Similar analyses as for the primary efficacy variable described in Section 8.3.7 using ANCOVA will be performed for the WPAI-Endometriosis exploratory efficacy endpoints.

#### ANALYSIS OF PROMIS FATIGUE SHORT FORM 6A

Similar analyses as for the primary efficacy variable described in Section 8.3.7 using ANCOVA will be performed for the change from CCI to CCI EOT in the PROMIS Fatigue Short Form 6a T-score.

#### ANALYSIS OF miRNA ANALYSIS

Similar analyses as for the primary efficacy variable described in Section 8.3.7 using ANCOVA will be performed for the change from baseline to CCI EOT in miRNA expression levels (miR-125b-5p, miR-451a, miR-3613-5p, miR-150-5p, miR-342-3p, and let-7b).

### 8.6. Analyses Supporting Secondary PD Objectives

#### 8.6.1. Secondary PD Endpoints

Serum hormone levels (LH, FSH, E2, E1, Progesterone) and androgens (testosterone, free testosterone, DHEA, and DHEAS) will be assessed at CCI /EOT.

#### 8.6.2. Intercurrent Event Handling and Data Imputation for Secondary PD Endpoints

See section 8.1.6, no missing data will be imputed for secondary PD/PK endpoints.

### 8.6.3. Analyses of Secondary PD Endpoints

Secondary PD endpoints will be analysed using the PD Analysis Set. Treatment comparisons between the OG-6219 dose groups and placebo will be conducted using ANCOVA on the change from baseline to CC and CC separately, with treatment as a fixed factor and the baseline value as a covariate. Estimated treatment differences with corresponding 95% CI and 2-sided p-values will be derived from the ANCOVA model. A multiplicative model will be used, i.e. the dependent variable and the covariate will be log-transformed before analysis and estimated treatment differences and 95% CI will be obtained by back-transformation.

## 8.7. Safety Analyses

### 8.7.1. Adverse Events

AEs will be coded using MedDRA coding dictionary, Version 25.1 or higher.

Treatment emergent adverse events (TEAEs) are defined as events that first occur or worsen (increase in severity) after the first dose of the study medication, during the Treatment Period, and up to 14 days (inclusive) after the last dose of study medication. Events starting on the day of first dose will be considered treatment-emergent unless information is available to indicate the event started prior to the time of first dose. In the case where it is not possible to define an AE as treatment emergent or not due to a partial start date, the AE will be classified by the worst case, i.e., treatment emergent. Pre-treatment AEs/SAEs starting before the on-treatment period, including those starting on the day of first dose of study medication yet prior to the study medication intake, will be excluded from the TEAE analyses (unless there is an increase in investigator assessed intensity or causality, or the AE meets SAE criteria post-treatment allocation).

An overview table of number of participants within each of the categories described in the sub-section below, will be provided. The broad AE categories consisting of the percentage of participants with any TEAE, a TEAE related to study treatment, a serious TEAE, a TEAE leading to treatment discontinuation, a TEAE leading to study discontinuation, an AE with an outcome of death, and an AESI will be summarized.

Listings will include all AEs, including those that were not treatment emergent.

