4.2 Scientific Rationale for Study Design

Organon is developing OG-6219 as a novel, HSD17 β 1 enzyme inhibitor for the treatment of moderate to severe ERP. The pharmacological action of OG-6219 is based on its potent and selective binding to HSD17 β 1. The OG-6219 is not expected to interfere with the biological effects of systemic circulating estrogen because the putative mechanism of action is based on its ability to inhibit local conversion of E1 to E2 in endometriotic lesions.

As part of a single/multiple ascending dose Phase 1 study, 37 pre-menopausal women treated with doses up to CCI BID of OG-6219 for 14 days showed the absence of effects on the HPG axis, along with demonstrating safety and tolerability up to the highest tested dose. FOR-1011 was identified as the primary and active metabolite of OG-6219, with a similar potency to inhibit HSD17 β 1 as the parent compound; OG-6219 and FOR-1011 have an additive effect on inhibition of HSD17 β 1. In Phase 1, FOR-1011 was found to accumulate and appeared to reach steady state within 14 days, the end of the treatment period in the Phase 1 study.

In this Phase 2a/b, multicenter, randomized, Placebo-controlled, double-blind, PoC, dose-range study in pre-menopausal women with moderate to severe ERP, the effect of OG-6219 on endometriosis-related OPP, DYS, NMPP, and QoL as measured by the EHP-30, a validated instrument in endometriosis patients, will be collected in the eDiary to assess the clinical efficacy of OG-6219. In addition, safety, and tolerability will be monitored. A 1 cycle safety follow-up period is implemented to exclude late effects on safety and tolerability and evaluate any possible residual therapeutic benefit.

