8.4.1 Time Period and Frequency for Collecting AE and SAE Information

All AEs and SAEs will be collected from the signing of the ICF until EOS at the time points specified in the SoA (Section 1.3).

All SAEs will be recorded and reported to the Sponsor or designee immediately and under no circumstance should this exceed 24 hours of the Investigator's awareness of the event, as indicated in Appendix 4. The Investigator will submit any updated SAE data to the Sponsor or designee within 24 hours of their awareness of the updated information.

From the time of screening (V1) through EOS/discontinuation, which is 30 days after last intake of study treatment, all AEs, SAEs, and other reportable safety events must be reported by the Investigator.

Additionally, any SAE brought to the attention of an Investigator at any time outside the period specified in the previous paragraph must be reported immediately (within 24 hours of learning about the event) to the Sponsor if the event is considered related to study treatment.

Investigators are not obligated to actively seek information on AEs or SAEs after conclusion of the study participation. However, if the Investigator learns of any SAE, including a death, at any time after a participant has been discontinued from the study, the event/cause of death is considered to be reasonably related to the study treatment or study participation, the Investigator must promptly notify the Sponsor or designee.

All initial and follow-up AEs, SAEs, and other reportable safety events will be recorded and reported to the Sponsor or designee within the time frames as indicated in Table 7.

The method of recording, evaluating, and assessing causality of AE and SAE and the procedures for completing and transmitting SAE reports are provided in Appendix 4.

Table 7 Reporting Time Periods and Time Frames for Adverse Events and Other Reportable Safety Events

Type of Event	Reporting Time Period: Screening (V1) to Pre-Treatment Allocation (C)	Reporting Time Period: Treatment Allocation (C) through Protocol-specified Follow-up Period	Time Frame to Report Event and Follow-up Information to Sponsor:
Nonserious Adverse Event (NSAE)	Report if: 
 Due to protocol-specified procedure Causes exclusion 	Report all	Per data entry guidelines

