9.4.7.1 Adverse Events

Adverse events will be coded using the most current version of Medical Dictionary for Regulatory Activities. All AEs, including those that are not treatment-emergent, will be listed. A TEAE is defined as an AE that is new or worsened in severity after the first dose of study treatment, including those events which begin during Safety Follow-up; events starting on the day of first dose will be considered treatment-emergent unless information is available to indicate the event started prior to the time of first dose. The timeframe for a TEAE after stopping the randomized treatment is 14 days. Treatment-emergent AEs will be summarized by system organ class, preferred term (PT), and treatment. Summaries by treatment group will be prepared for all AEs, TEAEs, and SAEs. A summary of TEAEs by severity will also be presented.

For summary tables, AEs coded to the same PT will be counted only once within a given participant. If an AE was recorded on multiple occasions in the same treatment period, only the highest severity and the highest degree of relationship to the study treatment will be

presented. If 2 or more clinical events were reported within a single AE entry, then the corresponding individual PT will be coded separately.

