#### 8.3.3.1. DEFINITION OF CYCLES

The definition of cycles for the calculation of averages over cycles are as follows:

- Screening cycle (SC) – starts at the start of menses associated with CCI and ends the day before the start of menses associated with CCI
- Baseline cycle (BC) – starts at the start of menses associated with CCI and ends at the day before the start of menses associated with CCI or the day of CCI whichever comes first.
- Treatment cycle 1 (TRC1) – starts at the day of CCI (randomization visit=day of first dose of randomized treatment) and ends the day before the start of menses associated with phone contact C (PC1).

- Treatment cycle 2 (TRC2) – starts at the start of menses associated with phone contact **C** and ends the day before the start of menses associated with **CCI**
- Treatment cycle 3 (TRC3) – starts at the start of menses associated with **CCI** and ends the day before the start of menses associated with **CCI** or, at the latest after **CCI** of randomized treatment.
- Safety follow-up cycle (SFC) – starts the day after the last dose of randomized treatment and ends 30 days after the last dose of randomized treatment.

Days after last dose of randomized treatment will only be included in SFC, and not in TRC1-TRC3.

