#### 8.7.1.4. SERIOUS ADVERSE EVENTS

Serious adverse events (SAEs) are those events recorded as 'Serious' on the Adverse Events page of the eCRF. A summary of serious TEAEs by SOC and PT will be prepared.

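### The SAP omits the by-arm all-AE and all-SAE summaries the protocol promises, so non-fatal, non-AESI events starting on days 15 to 30 after last dose are only listed

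*SAP*

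**What the plan says.** On tables, Protocol 9.4.7.1 states: "Summaries by treatment group will be prepared for all AEs, TEAEs, and SAEs". On the window, the same section counts as treatment-emergent events that are new or worse after first dose, "including those events which begin during Safety Follow-up". A little later it adds: "The timeframe for a TEAE after stopping the randomized treatment is 14 days".

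On collection, Protocol 8.4.1 has the investigator report AEs and SAEs "From the time of screening (V1) through EOS/discontinuation, which is 30 days after last intake of study treatment". SAP 8.3.3.1 gives the safety follow-up cycle the same length: it "starts the day after the last dose of randomized treatment and ends 30 days after the last dose of randomized treatment". Protocol 4.2 gives the reason for it: "A 1 cycle safety follow-up period is implemented to exclude late effects on safety and tolerability".

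The SAP takes the 14-day limit. Under SAP 8.7.1 a TEAE must start or worsen after first dose, "during the Treatment Period, and up to 14 days (inclusive) after the last dose of study medication". SAP 8.7.1.1 plans the main SOC/PT table for TEAEs. For serious events, SAP 8.7.1.4 states: "A summary of serious TEAEs by SOC and PT will be prepared". SAP 8.7.1.5 limits the SOC/PT table of fatal events to TEAEs. Events that are not treatment-emergent are mentioned only for the listings (end of SAP 8.7.1). SAP section 10 says that nothing was changed from the analyses planned in the protocol, apart from adding a description of the estimand.

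**The concern.** The protocol names three by-arm summaries. The SAP delivers one in full (TEAEs), narrows the second (SAEs become serious TEAEs) and drops the third (all AEs). It does not declare this.

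The events that fall out are those arising late in follow-up, which is the part of the study included to detect late effects. A reader of the study report would take the SAE table as the SAE rate by arm. An SAE on day 20 after last dose would have been collected and reported to the sponsor, but would not be in that rate. To compare arms over the last half of follow-up, someone would have to count lines in a listing.

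**Working it through.** The plan gives no figure of its own to reproduce on this point. The check is a comparison of texts plus simple window arithmetic.

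**Step 1. Promised against planned.**

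| By-arm summary in Protocol 9.4.7.1 | What SAP 8.7.1 to 8.7.1.6 plans |
|---|---|
| TEAEs | Planned (8.7.1.1), 14-day window |
| SAEs | Serious TEAEs only (8.7.1.4) |
| All AEs | No table; listing only |

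The general statement in SAP 8.1.1 that all data will be listed and summarised does not specify an all-AE or all-SAE table. The specific text in 8.7.1 sends non-emergent events to listings.

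**Step 2. The uncovered window.** Inputs: collection to day 30 after last dose (Protocol 8.4.1, SAP 8.3.3.1) and TEAE window to day 14 inclusive (SAP 8.7.1).

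- Uncovered days: 30 − 14 = 16 (days 15 to 30).
- Share of follow-up: 16/30 = 53%.
- Share of all time after randomisation, assuming three cycles of 21 to 32 days (Protocol 4.1) plus 30 days: the total is 3 × 21 + 30 = 93 to 3 × 32 + 30 = 126 days, and 16/126 to 16/93 is 13% to 17%.

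**Step 3. Where an event starting on day 20 after last dose would appear.**

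| Event | By-arm AE/SAE output |
|---|---|
| Non-fatal AE, not an AESI | None; listing only |
| Non-fatal SAE, not an AESI | None; listing only |
| Fatal AE | Overview row for AEs with fatal outcome (8.7.1), but not the SOC/PT table of fatal TEAEs (8.7.1.5) |
| AESI | Overview row (8.7.1) and AESI SOC/PT summary (8.7.1.6); the AESI proportion is limited to the on-treatment period |
| Laboratory change | Laboratory summaries and shifts (8.7.2) and liver criteria on post-baseline results (8.7.2.2), outside the AE tables |

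One exception runs the other way. An AE that cannot be classified because its start date is partial is treated as emergent, so a few late events could enter the TEAE tables.

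**Step 4. Scale, as illustration only.** The documents give no event rate for this period. Let r be an assumed 30-day risk after last dose, with constant hazard, 95 participants per arm (SAP 4.3) and no dropout. The risk over a 16-day window is 1 − (1 − r)^(16/30), and the expected number per arm is 95 times that.

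| Assumed r | 16-day risk | Expected participants per arm |
|---|---|---|
| 1% | 0.53% | 0.5 |
| 2% | 1.07% | 1.0 |
| 5% | 2.70% | 2.6 |
| 10% | 5.46% | 5.2 |

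The counts are small, but small counts matter for SAEs. Three such SAEs in one arm would be 3/95 = 3.2%, and the serious-TEAE table would show none of them.

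**The case against.** Several points against a stronger criticism are sound.

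- **The 14-day limit is not a SAP invention.** Protocol 9.4.7.1 states it. A reader might infer that the protocol flatly contradicts itself, but days 1 to 14 after last dose lie inside Safety Follow-up. The two sentences can therefore be read together as follow-up onsets counting up to day 14. The drafting is ambiguous and should be made single-valued, but it is not a clear contradiction.
- **The primary safety endpoint does not by itself require all-AE tables.** The objectives tables word it as any AE or SAE, which invites that inference. The statistical methods in the protocol synopsis, however, analyse it as the proportion with a TEAE, and the SAP follows that. The two wordings need reconciling.
- **Not every late signal is lost.** Deaths, AESIs (haemolysis among them) and liver laboratory abnormalities have by-arm outputs that are not cut at day 14, as shown in the working.
- **No data are lost.** Events are collected to day 30 and listed, and the DMC reviews unblinded safety data under a separate plan (SAP 7.1). AE reporting is descriptive, so no formal test is affected.

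These points narrow the concern without answering it. None of them supplies the all-AE and all-SAE summaries named in Protocol 9.4.7.1, and none makes the no-change statement in SAP section 10 accurate. DMC outputs are outside the scope of this SAP and do not fill the gap in its planned tables.

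**Conclusion.** The concern holds in limited form. The SAP departs, without saying so, from a protocol commitment to summarise all AEs and all SAEs by arm. The practical effect is confined to non-fatal AEs and SAEs that are not AESIs and that start or worsen on days 15 to 30: 16 of 30 follow-up days (53%), or about 13% to 17% of the time after randomisation. A related inconsistency concerns deaths, where the overview row covers any AE with a fatal outcome but the SOC/PT table covers only fatal TEAEs.

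The 16 days rest on the 30-day period in Protocol 8.4.1. Protocol 4.1 also ties the end-of-study visit to the next menses, so the length may vary between participants. The conclusion also takes the death and AESI rows at their wording, which does not restrict them to TEAEs. How many events are affected cannot be known from the documents. It should be corrected, because otherwise the by-arm SAE table would omit SAEs that the protocol said would be summarised.

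**What to change.** 1. Add to SAP 8.7.1 by-arm SOC/PT summaries of all AEs and of all SAEs, including fatal AEs, from first randomised dose to end of study.
2. Keep the 14-day TEAE tables as the on-treatment view, labelled as such.
3. Reconcile the two TEAE sentences in Protocol 9.4.7.1 so that one follow-up window defines a TEAE.
4. Align the AE/SAE wording of the primary safety endpoint in the objectives tables with the TEAE wording in the synopsis.
5. Make the death row of the overview table and the table in SAP 8.7.1.5 cover the same events.
6. Correct SAP section 10. If the sponsor chooses not to add the tables, that section should declare and justify the omission.

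The cost is SAP wording and a few extra tables from data already collected. No new assessments and no change to sample size are needed. The change is best made before the unblinding described in SAP 7.2; if made later, the tables should be identified as unplanned, as SAP section 2 requires.

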**8.7.1.1. ALL TEAEs**

Incidence of TEAEs will be presented by SOC and PT, with SOC in alphabetical order and PT in order of decreasing frequency. The incidence of TEAEs will be broken down further by maximum severity and relationship to study treatment.

The TEAE summary by SOC and PT will also be presented for the region subgroup.

**Severity**

Severity is classed as mild/ moderate/ severe (increasing severity). TEAEs with a missing severity will be classified as severe. If a participant reports a TEAE more than once within that SOC/ PT, the AE with the worst-case severity will be used in the corresponding severity summaries.

**Relationship to Study Treatment**

Relationship, as indicated by the Investigator, is classed as 'unrelated', 'unlikely to be related', 'possibly related', and 'probably related' (increasing severity of relationship). A 'related' TEAE is defined as a TEAE with a relationship to study treatment as 'possibly related' or 'probably related' to study treatment. TEAEs with a missing or 'unknown' relationship to study treatment will be regarded as 'related' to study treatment. If a participant reports the same AE as both related and unrelated within that SOC/ PT, the related AE will be used in the corresponding relationship summaries.

**8.7.1.2. TEAEs LEADING TO DISCONTINUATION OF STUDY TREATMENT**

TEAEs leading to permanent discontinuation of study treatment will be identified by using the 'Action taken with study treatment' variable equal to 'Drug withdrawal' from the AE page of the eCRF.

A summary of TEAEs leading to discontinuation of study treatment by SOC and PT will be prepared. A listing of all TEAEs leading to discontinuation of study treatment will be provided, along with the details as to whether the event was related or serious.

**8.7.1.3. TEAEs LEADING TO DISCONTINUATION FROM THE STUDY**

TEAEs leading to discontinuation from the study will be identified by using the 'Did the AE

cause the participant to discontinue from the study?' variable equal to 'Yes' from the AE page of the eCRF.

A summary of TEAEs leading to discontinuation from the study by SOC and PT will be prepared. A listing of all TEAEs leading to discontinuation from the study will be provided, along with the details as to whether the event was related or serious.

